8.5. Electrocardiograms

Summary statistics will be provided for heart rate, PR interval, QRS interval, QT interval, and QTcF at each visit. The investigator interpretation is collected as normal, abnormal not clinically significant (NCS), or abnormal clinically significant (CS). Patients whose interpretation shifts from normal to abnormal (CS or NCS) will be listed separately including description of the abnormality and any associated comments.

Categorical summaries will for baseline, worst post-baseline, and change from baseline for the following QTcF values will be presented:

- > 450 msec
- > 480 msec
- > 500 msec
- Change from baseline > 30 msec
- Change from baseline > 60 msec

CONFIDENTIAL

All ECG results will be presented in by-patient data listings. If applicable, cardiologist consult information will be presented in a separate by-patient data listing.

CONFIDENTIAL

9. Other Assessments

Other assessments will be provided in by-patient data listings only; no summary tables will be provided, including but not limited to the following:

- Eligibility details including unmet eligibility criteria
- Informed consent
- Randomization schema
- Physical examination collection information
- Serology
- Pregnancy testing
- FSH test
- Urine drug screen
- Alcohol test
- Urinalysis and Urine Microscopic Examination
- Coagulation
- Hemoglobin A1c
- Direct bilirubin
- Indirect bilirubin
- Laboratory reference ranges
- Cardiology consult
- Overdose
- Comments

Final, Version 2.0, 26JULY2023

CONFIDENTIAL

10. Changes to Protocol Planned Analyses

There were no changes from the protocol planned analyses.

CONFIDENTIAL

Statistical Analysis Plan CONFIDENTIAL Labcorp Drug Development Study: 000000231152 Protocol Reference: TERNCB-2002

11. Appendices

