- 20. Uncontrolled diabetes with HbA1c > 9.5%. Note: Patients with or without Type 2 diabetes may be enrolled provided all eligibility criteria are met
- 21. Unstable cardiovascular (CV) disease defined as myocardial infarction, unstable angina, percutaneous intervention, coronary artery bypass graft, or stroke within 6 months prior to randomization
- 22. Uncontrolled hyperlipidemia defined as fasting LDL cholesterol ≥ 150 mg/dL despite treatment or triglycerides > 500 mg/dL
- 23. LDL cholesterol < 40 mg/dL in patients who are not taking LDL cholesterol lowering therapy
- 24. Clinically significant abnormalities in 12-lead ECG at Screening, or known history of such abnormalities including but not limited to:
 - a. II/III-degree atrioventricular block or bundle branch block (right and left)
 - b. Arrhythmia (except occasional supraventricular premature beat)
 - c. QT-interval corrected for heart rate using Fridericia's method (QTc) > 450 msec for males or > 470 msec for females
 - d. Personal or family history of prolonged QT syndrome

Note: An ECG can be repeated in instances of lead placement error, incomplete or uninterpretable tracings, or suspicion of machine error at Screening

- 25. Known hypersensitivities to the study drugs (TERN-501 or TERN-101) or to any formulation excipients
- 26. Clinically significant multiple or severe drug allergies, intolerance to topical corticosteroids, or severe post-treatment hypersensitivity reactions
- 27. Known allergy, intolerance, or contraindication to beta blockers
- 28. Alcohol consumption of > 2 standard drinks per day for males and > one standard drink per day for females over a period of more than 3 consecutive months in the year prior to Screening. Remote history of alcoholism with abstinence > 12 months prior to Screening and no history of alcoholic liver disease is permissible

Note: A standard drink is defined as 12 oz (360 ml) beer (5% alcohol), 1.5 oz (45 ml) 80 proof liquor (40% alcohol), or 5 oz (150 ml) wine (12% alcohol)

29. Illicit substance/chemical abuse in the 12 months prior to Screening

CONFIDENTIAL

- 30. Cannabis use (tetrahydrocannabinol [THC] and cannabidiol [CBD]) within 14 days of randomization
- 31. Unwilling to abstain from excessive alcohol use (defined in exclusion criterion #28 above), cannabis use, and illicit substance use during study participation

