8.1.7. Cardiovascular Safety Monitoring

Cardiovascular safety will be monitored via vital signs (see Section 8.1.5) and 12-lead ECGs (see Section 8.1.6) along with clinical assessment of adverse events that may represent signs or symptoms of cardiac toxicity.

Signs and symptoms that may reflect cardiovascular toxicity include the following, with clinical significance to be determined by the Investigator:

- Vital signs changes including hypertension, hypotension, tachycardia, or bradycardia
- 12-lead ECG findings including tachycardia, bradycardia, atrial fibrillation or flutter, ventricular arrythmia, or QTc prolongation
- Clinical symptoms suggestive of cardiac ischemia or other cardiac dysfunction such as chest pain/pressure, palpitations, shortness of breath, or edema

Potential signs or symptoms consistent with cardiovascular toxicity should be carefully evaluated, with repeat of assessments (e.g., vital signs, ECG, laboratory values) to confirm findings and follow-up until resolution.

Signs or symptoms should be designated as AEs with CTCAE v5.0 severity determined per Appendix 6. Participant discontinuation of study drug criteria are outlined in Section 7.1.2.

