3.8.2. Definition of Baselines

The baseline value for statistical analyses of quantitative laboratory parameters is defined as the last non-missing assessment, including any unscheduled or repeat assessments, collected prior to the first administration of study drug, unless otherwise specified.

For glucose and lipid parameters, only assessments taken while fasting for 8 hours will be included in the baseline derivation.

The baseline value for analyses of qualitative parameters (e.g., normal/abnormal) is defined as the last evaluation prior to the first administration of study drug.

Final, Version 2.0, 26JULY2023

CONFIDENTIAL

The baseline value for analyses of weight, body mass index (BMI), and electrocardiogram parameters is defined as the last evaluation prior to the first administration of study drug.

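### The separate ECG listing in SAP 8.5 omits patients who worsen from abnormal, not clinically significant, at baseline to clinically significant on treatment, and no by-arm shift summary is planned

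*SAP*

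**What the plan says.** SAP 8.5 plans these ECG outputs:

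- Summary statistics by visit for heart rate, PR, QRS, QT and QTcF.
- A selective listing based on the investigator's three-level reading (normal, NCS, CS): "Patients whose interpretation shifts from normal to abnormal (CS or NCS) will be listed separately".
- QTcF threshold categories: "Categorical summaries will for baseline, worst post-baseline, and change from baseline for the following QTcF values will be presented".
- A full listing: "All ECG results will be presented in by-patient data listings".
- A separate listing of cardiologist consults, if there are any.

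No table of interpretation by treatment group is planned, either as a shift table or as a count of patients who worsen.

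On entry, Protocol 5.2, criterion 24, excludes patients with "Clinically significant abnormalities in 12-lead ECG at Screening, or known history of such abnormalities including but not limited to" a set of named conditions. One of these, arrhythmia, carries an exception for occasional supraventricular premature beats. A tracing read as abnormal but not clinically significant does not exclude a patient.

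Protocol 8.1.7 names the ECG findings that may reflect cardiovascular toxicity: "12-lead ECG findings including tachycardia, bradycardia, atrial fibrillation or flutter, ventricular arrythmia, or QTc prolongation". Protocol 2.3 describes excess systemic thyroid hormone stimulation, including its cardiovascular effects, as a key safety concern for any THR-β agonist.

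**The concern.** A selective safety listing should draw out the patients whose state became worse. On a three-level scale that means any move up the scale. The rule in SAP 8.5 is tied to a normal starting point, so it takes in a change that the investigator judged not clinically significant (normal to NCS) and leaves out one that the investigator judged clinically significant (NCS to CS).

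The omitted path is a plausible one. Take a patient who enters with occasional supraventricular premature beats, read as NCS, and who on treatment has atrial fibrillation, read as CS. Protocol 8.1.7 names that finding, yet the patient would not be in the selective listing. The QTcF categories would not pick up a rhythm change as such, and heart rate, PR and QRS receive only group summary statistics.

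At stake is how complete the ECG display is on a risk that the protocol itself singles out, in arms of about 20 patients where one or two individuals can colour the reading of an arm. Efficacy, type I error and sample size are not touched.

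**Working it through.** The plan states no figure to reproduce here, and the check is mainly one of logic.

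**Step 1. Where a patient can start.** Under SAP 3.8.2 the baseline for "electrocardiogram parameters is defined as the last evaluation prior to the first administration of study drug", and the rule given there for qualitative parameters is the same. The Schedule of Activities has an ECG at Screening and another before dosing at Week 0, so baseline is normally the Week 0 tracing. Criterion 24 removes patients with "Clinically significant abnormalities in 12-lead ECG at Screening" or a known history of them. Eligible patients should therefore start at normal or NCS.

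**Step 2. Which worsenings are possible, and which are listed.**

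| Baseline | On treatment | Separate listing in SAP 8.5 |
|---|---|---|
| Normal | NCS | Included |
| Normal | CS | Included |
| NCS | CS | Not included |

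Two of three worsening transitions are covered. For a patient who starts at NCS, the third is the only worsening the scale allows.

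The sentence does not say what the shift is measured from. I read it as baseline. If it meant any earlier visit, a patient who went from NCS to normal and then to CS would be caught, but one who went directly from NCS to CS still would not.

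**Step 3. Where else the omitted transition would appear.**

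- *Full ECG listing (SAP 8.5).* Yes, but with no flag. ECGs are scheduled at Screening and at Weeks 0, 2, 4, 6, 8, 12 and 16, which is 8 visits. If all 140 patients complete, that is 140 × 8 = 1,120 scheduled tracings.
- *QTcF categories (SAP 8.5).* Yes if the worsening is in QTc, since they apply whatever the baseline reading. They are not designed to show rhythm or conduction changes.
- *Adverse events.* Yes if reported. Protocol Appendix 6 treats an ECG that the investigator considers clinically significant, including one worse than at baseline, as meeting the AE definition. Protocol 8.1.7 asks that cardiovascular signs be designated as AEs and graded. SAP 8.2 lists all AEs and tabulates treatment-emergent ones by group.
- *Cardiologist-consult listing (SAP 8.5).* Only if a consult was obtained.

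**Step 4. Comparison with the laboratory plan.** SAP 8.3.5 also uses normal-to-abnormal shifts. But SAP 8.3.1 adds counts of patients whose CTCAE grade rises by at least 1 and by at least 2, and these do catch worsening from an abnormal baseline. ECG interpretation has no such second display.

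**The case against.** The strongest reply is that nothing is lost. The investigator who reads a tracing as CS is the person who must report the adverse event. The clause in Appendix 6 that keeps isolated abnormalities without symptoms out of AE reporting concerns laboratory tests, not ECGs. Treatment-emergent events are tabulated by arm, severity and relatedness, QTcF is categorised for everyone, and every tracing is listed. The selective listing is a supplementary display in a phase 2a trial, and its wording follows the convention of SAP 8.3.5. The first-in-human study reported no remarkable ECG findings, although that was in healthy subjects given repeat doses for only 14 days.

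Most of this stands, and it rules out several stronger readings that a reader might infer:

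- *That such a patient is never flagged, or can be found only by reading every tracing.* The documents do not support this. The AE route and the QTcF categories are both open to the patient.
- *That the listing misses the most serious change.* It does not. The largest move on the scale is normal to CS, and that is included.
- *That the group affected is large.* The documents give no prevalence of NCS tracings at baseline. An assumed 20% to 40% would give 0.2 × 140 = 28 to 0.4 × 140 = 56 patients, but that range has no source in the documents and makes no allowance for criterion 24. It also counts patients who start at NCS, not those who go on to CS.

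The reply does not make the rule complete. The AE route depends on a second entry by the investigator. SAP 8.4 says that clinically significant vital-sign abnormalities will be reported as adverse events, and SAP 8.5 has no matching sentence for ECGs. AE tables are organised by system organ class and preferred term and do not show the baseline reading. A complete ECG listing would also let a reviewer check that each new CS reading has a matching event. For patients who start at NCS, the listing as written does not allow that.

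**Conclusion.** The point holds in a narrow form. The selection rule in SAP 8.5 leaves out one of the three possible worsenings, NCS to CS, and no by-arm summary of interpretation shifts fills the gap. It is a minor defect in a safety display, not a failure to collect or report the signal: the worsening should reach the AE tables and is present, unflagged, in the full ECG listing. The size in patients cannot be derived, because the documents give neither the share of NCS tracings at baseline nor a rate of progression to CS.

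The conclusion rests on two readings: that the shift is measured from baseline, and that criterion 24 admits patients with NCS tracings, as its wording implies. It is still worth correcting, because the display concerns a risk that the protocol calls key and the data are already collected.

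**What to change.** In SAP 8.5, replace the selection rule with one that lists patients whose ECG interpretation worsens from baseline: normal to NCS, normal to CS, or NCS to CS. Naming baseline as the reference also removes the ambiguity noted above.

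Add one table by treatment group that cross-classifies baseline interpretation (normal, NCS, CS) against worst post-baseline interpretation. The denominator would be patients with a baseline and at least one post-baseline reading. State whether unscheduled tracings count towards the worst reading, since Protocol 8.1.6 provides for additional ECGs when symptoms suggest a cardiac cause.

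The cost is one changed selection condition, a slightly longer listing and one extra table. No new data are needed, and no endpoint, test or site procedure changes.

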Appendix 1: Document History

Document Version, Status, Date	Summary / Reason for Changes
Version 0.1, Draft, 12AUG2022	Not applicable; the first version
Version 0.2, Draft, 30SEP2022	Addressed sponsor comments from Version 0.1
Version 0.3, Draft, 18JAN2023	Addressed sponsor comments from Version 0.2
Version 0.4, Draft, 13MAR2023	Addressed sponsor comments from Version 0.3
Version 0.5, Draft, 05MAY2023	Addressed sponsor comments from Version 0.4
Version 0.6, Draft, 18JUL2023	Addressed sponsor comments from Version 0.5 and TLF shells version Draft 0.3
Version 1.0, Final: 20July2023.	Comments from version 0.6 addressed and SAP signed off
Version 1.1 Final 26July2023	Additional changes requested by sponsor after sign off.
Version 2.0 final 26Jluy2023	Resolved final formatting comments

Labcorp Drug Development Study: 000000231152 Protocol Reference: TERNCB-2002

APPENDIX 2: IMPUTATION RULES FOR MISSING OR PARTIAL DATES FOR ADVERSE EVENTS AND CONCOMITANT MEDICATIONS

Date	Situation	Imputation Rule
Start Date	Only month and year are known and month and year are prior to first dose date	Use the last day of the month
	Only month and year are known and month and year are the same as first dose date	Use the first study drug administration date
	Only month and year are known and month and year are after first dose date	Use the first day of the month
	Only year is known and year is before first dose date	Use Dec 31 of that year
	Only year is known and year is same as first dose date	Use the first study drug administration date
	Only year is known and year is after first dose date	Use Jan 1 of that year
	Entire date is missing	Use the first study drug administration date
	The estimated start date is after a complete or imputed AE stop date	Use the first day of the month of the AE stop date
Stop/End Date	Only month and year are known and month and year are prior to last dose date	Use the last day of the month
	Only month and year are known and month and year are the same as last dose date	Use the last dose date
	Only month and year are known and month and year are after last dose date	Use the last day of the month
	Only year is known and year is before last dose date	Use Dec 31 of that year
	Only year is known and year is same as last dose date	Use the last study drug administration date
	Only year is known and year is after last dose date	Use Dec 31 of that year
	Entire date is missing	Use the last study drug administration date
	The estimated stop date is before a complete or imputed AE start date	Use the last day of the month of the AE start date
AE = adverse ev	vent, Dec = December, Jan = January	

CONFIDENTIAL

Statistical Analysis Plan CONFIDENTIAL Labcorp Drug Development Study: 000000231152 Protocol Reference: TERNCB-2002

APPENDIX 3: ABBREVIATIONS

Abbreviation or Special Term	Explanation
7αC4	7α-hydroxy-4-cholesten-3-one
ADaM	Analysis Data Model
AE	adverse event
ALP	alkaline phosphatase
ALT	alanine transaminase
ANCOVA	analysis of covariance
AST	aspartate transaminase
ATC	Anatomical Therapeutic Class
AUC	area under the concentration-time curve
BLQ	below limit of quantification
BMI	body mass index
CAP	Controlled Attenuation Parameter
CAP	
	Clinical Data Interchange Standards Consortium
CHG CI	change from baseline ADaM basic dataset structure defined variable confidence interval
CK-18	
	cytokeratin-18
COVID-19	Coronavirus disease 2019
Cmax	maximal concentration
CRF	case report form
CSR	clinical study report
CTCAE	Common Terminology Criteria for Adverse Events
CTMS	clinical trial management system
CV	coefficient of variation
DPP-4	Dipeptidyl peptidase 4
eGFR	estimated glomerular filtration rate
eCRF	electronic case report form
ECG	electrocardiogram
ET	early termination
FDA	Food and Drug Administration
FGF	fibroblast growth factor
FIB-4	Fibrosis-4 Score
FSH	follicle stimulating hormone
FXR	farnesoid X receptor
GGT	gamma-glutamyl transpeptidase
GLP-1	Glucagon-like peptide-1
HA	hyaluronic acid
HDL	high-density lipoprotein
hs-CRP	high sensitivity C-reactive protein
ICF	informed consent form
ICH	International Council for Harmonisation
IG	implementation guide
IMP	investigational medicinal product
INR	international normalized ratio
IWRS	interactive web response system
LDL	low-density lipoprotein

Labcorp Drug Development Study: 000000231152 Protocol Reference: TERNCB-2002

Abbreviation or Special Term	Explanation
LFC	liver fat content
LFT	liver function test
LLN	lower limit of normal
ln	natural log
LOCF	Last observation carried forward
LS	least squares
MedDRA	Medical Dictionary for Regulatory Activities
MMRM	mixed model for repeated measures
MRI-PDFF	Magnetic Resonance Imaging Proton Density Fat Fraction
NAFLD	non-alcoholic fatty liver disease
NAS	non-alcoholic fatty liver disease activity score
NASH	non-alcoholic steatohepatitis
NC	not calculated
NCA	noncompartmental analysis
NCI	National Cancer Institute
PCHG	percent change from baseline ADaM basic dataset structure defined
	variable
PIIINP	procollagen III n-terminal propeptide
PD	pharmacodynamics
PK	pharmacokinetics
PRO-C3	pro-peptide of type III collagen
Q1	25th percentile, first quartile
Q3	75th percentile, third quartile
QTcF	QT corrected for heart rate by Fridericia's cube root formula
REML	restricted maximum likelihood
SAE	serious adverse event
SAP	statistical analysis plan
SARS-CoV-2	severe acute respiratory syndrome coronavirus 2
SD	standard deviation
SDG	Standardized Drug Grouping
SDTM	Study Data Tabulation Model
SE	least squares mean standard error
SGLT-2	Sodium-glucose co-transporter 2
TEAE	treatment emergent adverse event
TERN-101	investigational agonist of Farnesoid X receptor
TIMP-1	tissue inhibitor of metalloproteinases-1
ULN	upper limit of normal
WHODD	World Health Organization Drug Dictionary

CONFIDENTIAL
